# 1 PROTOCOL SUMMARY

## 1.1 SYNOPSIS

Sponsor-Investigator:	[name]
Study Title:	TeXan Allergy & Sinus Center Mountain Cedar Intra-Lymphatic Immunotherapy Study (TX-SMILE)
Study Description:	
TX-SMILE is an investigator-initiated, multi-center, randomized, double-blind, parallel-group, placebo-controlled study to evaluate the safety, tolerability, and efficacy of an alternative injection site and associated adjustments to dosing and treatment regimen for allergen immunotherapy with a commercially-available, FDA-approved allergenic extract (ALK-Abelló, Inc., Port Washington, NY 11050; US Government License No. 1256) for the immunotherapy treatment of allergic rhinitis and conjunctivitis due to pollen from the conifer Mountain Cedar (Juniperus ashei).
 
The purpose of this study is to evaluate the effect of a three-dose treatment series of ultrasonography-guided, intra-lymphatic immunotherapy injections over a two-month period prior to the start of the 2018-2019 Mountain Cedar allergy season in central Texas. Patients will be evaluated for safety and tolerability during the treatment period and for efficacy during the 2018-2019 Texas Mountain Cedar pollen season.

Study Number:	TASC-ILIT-MC-2018
IND Number:	18-643
NCT Number:	NCT03682965
General Study Design:	TX-SMILE is an investigator-initiated, multi-center, randomized, double-blind, parallel-group, placebo-controlled study to evaluate the safety, tolerability, and efficacy of intra-lymphatic administration of an approved allergenic extract for the immunotherapy treatment of allergic rhinitis and conjunctivitis due to pollen from the conifer Mountain Cedar (Mountain Cedar pollinosis).
Background:	
More than 40 million people in the United States (approximately 14% of adults and 13% of children) and more than 400 million people worldwide experience allergic rhinitis (AR). AR can substantially reduce patients' quality of life and can impair many aspects of physical and social well-being, including reduced school and work performance. Furthermore, patients with AR experience significant out-of-pocket medication costs and make nearly twice as many visits to health care providers as matched controls. The disease manifestations of AR include both nasal and non-nasal symptoms. The primary nasal symptoms are nasal itching, sneezing, rhinorrhea, and congestion, while the major non-nasal symptoms include itchy watery, red, and/or swollen eyes, earache, headache, cough and irritation of the palate. AR is also an independent risk factor for the development of asthma and it is reported that 38% of American patients with AR have asthma and up to 78% of American asthma patients have AR.

	
For regulatory purposes, allergic rhinitis is differentiated into two related disorders, seasonal AR and perennial AR. The pathophysiology of SAR and PAR are similar in terms of the chemical mediators involved and clinical manifestations, with the differences between the two primarily based on the cause and duration of disease. Although there are many treatments available, including over-the-counter remedies for reduction of symptoms of AR, allergen immunotherapy (AIT) is the only treatment option that can provide significant improvements in allergic symptoms and reduce the need for pharmacotherapy. Since it was introduced in 1911, AIT has been clinically shown to provide long-term benefits, including symptomatic disease remission and a reduction in allergic disease progression from rhinitis to asthma. The World Health Organization recognizes allergen immunotherapy as the only allergy treatment for AR that currently treats the underlying disease rather than just the disease symptoms.
 
Conventional AIT involves a dose-escalation series of thirty (30) to seventy (70) subcutaneous injections of over period of three (3) to five (5) years, leading to relief of allergy symptoms by inducing tolerance to the allergen, reducing or eliminating the natural immune response. However, this regimen presents barriers to patient adherence, including the time commitment required to complete therapy. Thus, fewer than 5% patients with serious AR symptoms that could benefit from immunotherapy receive AIT treatment.
 
A variety of allergen extracts are FDA-approved for immunotherapy based on individualized subcutaneous dosing (subcutaneous immunotherapy; SCIT) determined by the treating clinician based on patient sensitivity, clinical response, and tolerance to the extract during the early phases of an injection regimen. In 2008, Senti and colleagues first reported on an alternative treatment regimen for AIT involving the administration of allergenic extract directly into the lymph nodes, the proposed site of action for SCIT. This route is called Intra-lymphatic Immunotherapy (ILIT) and since that initial clinical trial, several additional randomized controlled trials of ILIT have been conducted and generally demonstrate more rapid tolerization at lower doses than conventional SCIT but with similar safety and tolerability.


Objectives:
	
 
1. To evaluate the systemic safety of ILIT for Mountain Cedar pollinosis relative to intranodal injections of placebo control based on the proportion of subjects receiving allergenic extract versus the proportion of subjects receiving placebo:             
 
a. experiencing anaphylaxis, or
 
b. treated with epinephrine, or
 
c. Experiencing any other treatment-emergent, serious adverse event (SAE) within 60 minutes of the procedure.
 
 
 
2. To evaluate the safety profile of ILIT versus placebo using a standardized scoring system for systemic AEs of interest (AEIs) up to 60 minutes post-procedure
 
3. To evaluate the efficacy of ILIT relative to placebo during the 2018-2019 Texas Mountain Cedar allergy season as assessed by the daily
 

	
total combined score (TCS), a composite of the Daily Symptoms Score (DSS) and Daily Medication Score (DMS).
 
 
To evaluate the tolerability of ILIT using a patient-reported outcome measure
 
To assess the patients' self-reported satisfaction with treatment at the end-of-study.
 
To assess the induction of tolerance to the causative allergen using allergen-specific serum IgE testing
 

Endpoints:	
Primary Efficacy Endpoint:
 
 
Average daily TCS during the 2018-2019 Mountain Cedar pollen season
 
 
Secondary Efficacy Endpoints:
 
 
Proportion of days during pollen season for which active patients experience a lower TCS than placebo patients
 
Patient reported pain or discomfort immediately after and 30 minutes post ILIT procedure
 
Patient-reported treatment satisfaction at the end of the study
 
Reduction in skin reactivity assessed using allergenic-specific serum IgE testing from pre-treatment to post-treatment (the end-of-study visit)
 
 
Exploratory Endpoints:
 
 
Use of rescue inhalers by patients with stable asthma
 
 
Safety Endpoints:
 
 
Proportion of subjects experiencing a serious, treatment-emergent AE up to 60 minutes after an intranodal injection procedure
 
Proportion of subjects experiencing systemic reactions to ILIT relative to placebo and severity of reactions relative to placebo as assessed by the Total Safety Score (TSS)
 
Proportion of subjects reporting local injection site reactions relative to placebo and severity of local reactions relative to placebo, as assessed by the TSS
 

Study Population:	
This study will include up to 40 screened and 32 enrolled adult patients aged 18 or older with seasonal allergic rhinitis (SAR) and conjunctivitis due to pollen from the conifer Mountain Cedar (Juniperus ashei).

Key Inclusion Criteria:	
 
Both male and female adult patients with a history of SAR with bothersome symptoms due to Mountain Cedar pollinosis confirmed using the Modified Quantitate Test (MQT; defined as a wheal greater than or equal to 3 millimeters larger than the diluent control)a
 
Patients must be willing to provide written, informed consent
 
Patients must be willing and able to comply with study procedures
 
Women of childbearing potential must agree to use an acceptable form of contraception during the trial
 

Key Exclusion Criteria:	
 
Patients less than 18 years of age
 
Clinically-significant chronic sinusitis, as determined by the investigator
 

	
 
3. History of systemic allergic reaction, e.g. anaphylaxis with cardiorespiratory symptoms, generalized urticaria, or severe facial angioedema.
 
4. Participation in another clinical trial or use of an experimental medication within 30 days of enrollment
 
5. Medically significant co-morbidities that, in the opinion of the investigator, place the subject at increased risk during the study or may confound the interpretation of results, including but not limited to:             
 
a. Autoimmune diseases, other than AR, stable allergic asthmac, eczema and food sensitivities
 
b. Pulmonary or respiratory diseases other than stable asthma
 
c. Cancer other than basal cell carcinoma
 
d. Coronary artery disease or hypertension treated with beta-blockers
 
e. Clinically significant impairment of renal or hepatic function
 
f. Clinically-significant lab abnormalities
 
 
 
6. Use of concomitant medications that, in the opinion of the investigator, may reduce the effectiveness of rescue treatments for anaphylaxis (e.g. beta-blockers) or alter the immune response to AIT (e.g., immunosuppressants, systemic corticosteroids)
 
7. Previously completed SCIT or SLIT for Mountain Cedar pollinosis, that in the opinion of the investigator would interfere with the assessment or treatment of the patientb
 
8. Inability to access suitable lymph nodes for ILIT injections
 
9. Plans to leave the area for a significant period of the upcoming Mountain Cedar pollen season
 
10. Pregnant or lactating females
 

Study Phase and Stage of Development	
Mountain Cedar pollen allergenic extract (ALK-Abelló, Inc., Port Washington, NY 11050; US Government License No. 1256) is an FDA-approved, commercially available product. This investigation is a phase 2 proof-of-concept study to evaluate an alternative injection site location (inguinal lymph node versus subcutaneous injection into the upper aspect of the arm) with an associated reduction in the extract dose and number of injections.

Sites/ Facilities Enrolling Participants:	
Up to sixteen (16) centers in the United States, that are affiliated with Texan Allergy & Sinus Center will recruit patients. Enrolled subjects will receive treatment at one of three (3) TASC ambulatory surgical centers in San Antonio, Dallas, and Austin, Texas.

Study IRB of Record	
IntegReview IRB [name]
 
IRB Organization (IORG) number: IORG0000689

Description of Study Intervention:	
After informed consent subjects will be randomized 1:1 to receive a series of three (3) injections (0.1 mL) of the allergenic extract (Mountain Cedar Pollen, ALK-Abelló, Inc., Port Washington, NY 11050; US

[figure not shown]
	Government License No. 1256) or diluent as placebo control (sterile saline solution containing 0.4% phenol as a preservative; ALK-Abelló, Inc., Port Washington, NY) every four weeks into a superficial inguinal lymph node through guidance via ultrasonography using a 1-mL hypodermic syringe with a 25-gauge or smaller needle.
Study Duration:	The treatment period will be up to three (3) months, followed by three (3) months of follow-up beginning prior to the start of the 2018-2019 Texas Mountain Cedar allergy season and concluding at the end of the season. The total study duration will therefore be from approximately September 2018 thru August 2019 for completion of data analysis. Study results will be reported within 12 months of study completion.
Participant Duration:	Patients will receive a series of three ILIT injections four weeks apart prior to the start of the 2018-2019 Texas Mountain Cedar allergy season and will be followed monthly for up to four months. The end-of-study visit will be scheduled to take place after the pollen season has ended, as determined by the daily pollen count measures recorded at each participating center. The total study duration for individual participants will be less than seven months.

a Patients that are hypersensitive to Mountain Cedar allergenic extract as defined in section 5.2 (a wheal for allergenic extract greater than that for the positive control), the initial during skin testing are clinically the most likely to benefit from AIT and will therefore be allowed to enroll. Starting doses for these patients are reduced in accordance with section 6.2.

b Patients that previously began but did not complete adequate AIT treatment for Mountain Cedar allergy and meet the other inclusion and exclusion criteria will be eligible at the discretion of the investigator.

c Patients with asthma will require documentation that their asthma is well controlled using ACT score and/or normal spirometry to be eligible. Patients with poorly controlled asthma are defined as those with frequent use of short-acting beta agonists (SABA), night-time awakenings, reduction in normal activity levels per the National Asthma Education and Prevention Program, Third Expert Panel on the Diagnosis and Management of Asthma, or have any history of a life-threatening asthma attack, hospitalization or who have sought clinical intervention for asthma including use of oral corticosteroids within the past three (3) months, or have a lung function measured by FEV1 of less than or equal to 70% of the predicted value while on their usual asthma medication.

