1.2 SCHEMA AND TIMELINE

### 1.3 SCHEDULE OF EVENTS

Procedures	Screening Visit	Treatment			Follow-up	
	Day -21 to Day 1	Treatment Visit 1 c Day 1	Treatment Visit 2 Day 28 +/-3	Treatment Visit 3 Day 56 +/-6	Patient Diary Approx. Dec 2018 to March 2019	End-of-Study Visit 4 March – April 2019
Informed consent	X					
Demographics	X					
Medical history	X					
Physical exam	X					X
Modified Quantitative Test	X					
Allergen-specific Serum IgE	X					X
Vital signs a	X	X	X	X		
Urine pregnancy test b	X	X	X	X		
Eligibility Assessment	X					
Randomization	X					
Intralymphatic Injection (allergenic extract or placebo)		X	X	X		
Pain and discomfort (NRS-11)		X	X	X		
Adverse Event review	X	X	X	X		X
Total Safety Score		X	X	X		
DSS and DMS					X	
Review patient diary data						X
Treatment satisfaction						X
Concomitant Medication Review	X	X	X	X	X	X
Complete Case Report Forms (CRFs)	X	X	X	X	X	X

a Vital signs at treatment visits to be performed before injection and every fifteen minutes post-injection for sixty (60) minutes.

b Urine pregnancy testing only for women of childbearing potential.

c Screening and Treatment Visit 1 may be combined in some circumstances. In such cases, procedures specific to both should be completed.

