## 8.3 ADVERSE EVENTS AND SERIOUS ADVERSE EVENTS

### 8.3.1 DEFINITION OF ADVERSE EVENTS (AE)

Any untoward medical occurrence in a clinical investigation subject administered immunotherapy or matched placebo which does not necessarily have a causal relationship with the treatment and is not otherwise related to their underlying medical condition or a comorbid condition present at the time of enrollment. An AE can therefore be any unfavorable and unintended sign, symptom, or disease temporally associated with the use of the immunotherapy or other medicinal product, whether or not related to the medicinal product, that has an onset after enrollment in the study and the initiation of treatment, defined as the injection of study treatment and the seven day period following. Events reported via the patient diary on the daily symptom score are by definition symptoms of the underlying disease and are therefore not adverse events. Symptoms may fluctuate and thus changes in symptoms are not considered adverse events but are rather measures of treatment efficacy for the underlying condition. Pre-planned procedures are not considered adverse events. Pre-existing conditions, unless worsened are not considered adverse events. Whenever possible, adverse events will be consolidated into the underlying diagnosis rather than a collection of separately reported symptoms, as determined by the investigator.

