## 8.3.4 TIME PERIOD AND FREQUENCY FOR EVENT ASSESSMENT AND FOLLOW-UP

The occurrence of an adverse event (AE) or serious adverse event (SAE) may come to the attention of study personnel during study visits and interviews, or other contacts with a study participant during the treatment and follow-up period.

All AEs will be captured on the appropriate case report form (CRF). Information to be collected includes event description, date of onset, clinician’s assessment of severity, relationship to study product as assessed by the investigator, and date of resolution/stabilization of the event. All AEs occurring while on study must be documented appropriately, according to the definitions in Section 8, regardless of

relationship. All AEs will be followed to adequate resolution or the end-of-the study. Local and systemic reactions during the 60-minute observation period will be captured on the Total Safety Score report form which includes specific criteria for assessing and grading adverse reactions to AIT. For patients experiencing a reaction, the observation period will be extended until the patient is stable. In accordance with Section 2.1, after each treatment visit, patients are counseled on how to recognize the signs of delayed-onset reactions, including worsening pain, tenderness, redness, swelling at the injection site and to assess the injection site for these symptoms for seven (7) following treatment. If they recognize these or other symptoms of a delayed-onset reaction, they are instructed to report these symptoms by phone.

Any medical condition that is present at the time that the participant is screened will be considered as baseline and not reported as an AE. However, if the study participant's pre-existing condition deteriorates at any time during the study, it will be recorded as an AE.

Changes in the severity of an AE will be documented to allow an assessment of the duration of the event at each level of severity to be performed. AEs characterized as intermittent require documentation of onset and duration of each episode.

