The investigator or designee will record all events, defined as serious, unexpected, and related adverse drug reactions with start dates occurring any time after the initiation of treatment until seven (7) days after the third treatment will be reported in accordance with the requirements of 21 CFR 312, if applicable, to the manufacturer using their post-marketing safety report system, and to the IRB as an Unanticipated Problem in accordance with Section 8.4. At each study visit, the investigator will inquire about the occurrence of AE/SAEs since the last visit. Unresolved adverse events will be followed for outcome information until the end of the study.

---

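### The synopsis promises monthly follow-up, but no adverse-event inquiry is scheduled between the third injection and the end-of-study visit, roughly 3 to 5 months later

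*Protocol*

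**What the plan says.** **Follow-up promised.** The Participant Duration row of the synopsis says that patients "will be followed monthly for up to four months". The Study Duration row just above it gives a different length: "followed by three (3) months of follow-up beginning prior to the start of the 2018-2019 Texas Mountain Cedar allergy season".

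**Follow-up scheduled.** The Schedule of Events has two follow-up columns. One is the remote diary ("Patient Diary Approx. Dec 2018 to March 2019") and the other is a single end-of-study visit in March–April 2019. Adverse-event review is marked at screening, at the three treatment visits and at end of study. It is blank in the diary column, where concomitant-medication review and CRF completion are marked. Protocol sections 8.1.1.4 to 8.1.1.6 go straight from Treatment Visit 3 to the diary and then to the end-of-study visit. The SAP visit-window table (section 7.3) has the same columns.

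**How adverse events are found.** Under protocol section 8.3.4 the investigator asks about events at each study visit. Between visits, patients are told to watch the injection site for seven days (the unit is missing in the text), and if they notice a delayed reaction "they are instructed to report these symptoms by phone". Section 8.3.1 limits onset to the injection and the seven days after it. Section 8.3.4 likewise covers start dates "until seven (7) days after the third treatment". The diary cannot fill the gap as written: "Events reported via the patient diary on the daily symptom score are by definition symptoms of the underlying disease", and section 8.3.1 therefore does not count them as adverse events.

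**The concern.** The structured safety worksheet stops at 60 minutes, yet the protocol expects that some reactions matter later. Section 2.3.1 says that systemic reactions may occur at any time after immunotherapy. It also treats local injection-site reactions as significant only if they last at least 24 hours, which a 60-minute observation cannot show. Such reactions can only be learned of through later contact.

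For the first two injections that contact comes at the next treatment visit, about four weeks on. For the third, the patient is next asked months later and must then place a possibly minor event within one particular week of the previous autumn or early winter. If the patient does not phone, the sponsor cannot tell silence from absence of a reaction. If all 32 planned patients complete the series, this applies to 32 of 32 × 3 = 96 injections.

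Two things are at stake. One is the completeness of the adverse-event table in SAP section 10.2. The other is how soon the sponsor learns of an event that would trigger the study hold in protocol section 8.2. This is also, by the protocol's own account (section 2.2), the first trial of the intralymphatic route for this allergen.

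**Working it through.** No power or sample-size figure enters here. The check is a count of contacts plus calendar arithmetic.

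**1. Contacts.** Monthly follow-up for up to four months implies up to 4 contacts. The schedule, the visit text and the SAP table give 1 visit with adverse-event review after injection 3.

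**2. Gap after injections 1 and 2.** Windows are from protocol section 1.3: injection 1 on Day 1, injection 2 on Day 28 ± 3 (Days 25–31), injection 3 on Day 56 ± 6 (Days 50–62).

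- After injection 1: 25 − 1 = 24 to 31 − 1 = 30 days.
- After injection 2: 50 − 31 = 19 to 62 − 25 = 37 days.

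**3. Gap after injection 3.** Gap = end-of-study date (1 March to 30 April 2019) minus injection 3 date (Day 1 + 49 to Day 1 + 61 days). Months = days / 30.4375. The documents give no calendar date for Day 1, so it is an assumption. The synopsis dates the study "from approximately September 2018 thru August 2019 for completion of data analysis". Protocol section 6.2.3 gives patient vials six months' stability and an expiry of 28 March 2019, which points to preparation around 28 September 2018. I take that as the base case and 1 September and 15 October as outer cases.

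| Assumed Day 1 (2018) | Injection 3 | Shortest gap | Longest gap | Months |
|---|---|---|---|---|
| 1 Sep | 20 Oct–1 Nov | 120 days | 192 days | 3.9–6.3 |
| 28 Sep | 16–28 Nov | 93 days | 165 days | 3.1–5.4 |
| 15 Oct | 3–15 Dec | 76 days | 148 days | 2.5–4.9 |

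**4. Check against the stated maximum.** The synopsis also says: "The total study duration for individual participants will be less than seven months". Counted from Day 1, seven months is 7 × 30.4375 = 213 days, so the gap can be at most 213 − 49 = 164 days, or 5.4 months. The 192-day case breaks that limit (1 September to 30 April is 241 days, 7.9 months), and the longest base-case gap sits at it. Roughly 3 to 5 months is therefore a fair summary.

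**5. Ratio at nominal dates.** With Day 1 on 28 September, injection 3 falls on 22 November and the gap is 99 to 159 days. The nominal gap after injection 2 is 56 − 28 = 28 days. The ratio is 99/28 = 3.5 to 159/28 = 5.7.

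**6. Relation to the onset window.** In the base case the first scheduled question comes 93 − 7 = 86 to 165 − 7 = 158 days after the seven-day window has ended.

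**The case against.** The strongest reply is that little of consequence depends on this gap, and much of that reply stands.

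- **Primary safety result.** Because safety is the primary objective, a reader might infer that the primary result is weakened. It is not. The primary endpoint and the Total Safety Score objective are defined up to 60 minutes after the procedure (protocol section 3), and all three injections are observed identically for that hour.
- **Reporting deadline.** A reader might infer that a late-discovered reaction falls outside its reporting window. Section 8.3.4 limits events by start date and sets no deadline for discovery. Section 8.4.2 counts from discovery and covers unanticipated problems found after study completion. Late awareness is a fair worry, but a closed window is not.
- **Comparison between injections.** A reader might infer that unequal ascertainment spoils a planned comparison of injections. SAP section 10.2 summarises spontaneous reports by body system and treatment group, not by injection. Poor recall should affect both blinded arms, so under-counting is likelier than a directional bias.
- **Other contacts.** The months are not silent. Patients are counselled to phone in, the diary column includes concomitant-medication review, persistent diary non-responders are called (section 6.4), and section 8.3.4 allows events to surface at any contact. None of these, however, is a scheduled adverse-event question.
- **Missing figure.** The figure under section 1.2 is not readable in the text available and might show follow-up contacts. The visit-by-visit text lists none, so this lowers certainty only slightly.

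What remains is the contradiction between synopsis and schedule, and the absence of any scheduled inquiry after injection 3 until end of study.

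**Conclusion.** The point holds as an inconsistency in the protocol and a modest gap in active adverse-event inquiry. Staff ask about events 24–30 and 19–37 days after injections 1 and 2, but roughly 3 to 5 months after injection 3. The full range is about 2.5 to 6.3 months and rests on the assumed Day 1; its upper end conflicts with the protocol's own limit on participant duration. None of the start dates examined brings the third gap near four weeks.

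The likely effects are some under-counting of delayed events after the third injection, probably in both arms, and later sponsor awareness of an event relevant to the hold rule. The documents give no rate of delayed reactions to this extract by this route, so the number of events missed cannot be estimated. The documents do not support going further, to a compromised primary safety endpoint or a lapsed reporting obligation.

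**What to change.** 1. Reconcile the synopsis, the Schedule of Events, and sections 8.1.1.5 and 8.3.4 on the number, timing and adverse-event content of follow-up contacts, and settle whether follow-up lasts three months or up to four. Either add an adverse-event question to the monthly contacts that the synopsis promises, or correct the synopsis to match the schedule.
2. Mark adverse-event review in the follow-up period of the schedule. Send one structured yes/no item about 7 days after injection 3, asking about any new or worsening reaction or health problem since the injection. A yes prompts the site to complete the adverse-event form.
3. Time the item from the date of injection 3, not from the opening of the diary. In the base case, day 7 falls between 23 November and 5 December, around the approximate diary start. The EDC system already sends texts and emails (section 6.4), and contact details are reconfirmed at Treatment Visit 3 (section 8.1.1.4).
4. State that the item lies outside the daily symptom score, so that section 8.3.1 does not exclude the answers.

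Day-7 items after injections 1 and 2 are optional: events are already asked about at the next visit, and patients are not instructed on the diary until Treatment Visit 3.

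The cost is one extra message per patient, a few more minor events to record in both arms, and occasional follow-up calls. No dose, treatment or clinical rule changes.
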